8.2.2. Vital Signs

Vital sign measurements will be taken after the participant has been resting in the supine or semi-recumbent position for at least 5 minutes and will include temperature (°C; tympanic or oral), respiratory rate, blood pressure, and pulse.

The timing of vital sign measurements is described in the SoA (Section 1.3). Of note, vital signs measurements will be performed every 15 minutes for the first hour after dose administration to monitor for anaphylaxis.

Out of range blood pressure or pulse measurements will be repeated at the Investigator's discretion. Confirmed, clinically significant vital sign measurements will be recorded as AEs.

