8.2.4. Clinical Safety Laboratory Assessments

All protocol-required assessments, as defined in Section 10.2, must be conducted in accordance with the SoA (Section 1.3) and the Laboratory Manual. Clinical and laboratory assessments to assess safety will be performed by a central laboratory.

• The Investigator must review the laboratory report, document this review, and record any clinically relevant changes occurring during the study in the AE section of the eCRF. The laboratory reports must be filed with the source documents. Clinically

Page 51 of 97	
Alexion Confidential	

significant abnormal laboratory findings are those which are not associated with the underlying disease, unless judged by the Investigator to be more severe than expected for the participant's condition.

- All laboratory tests with values considered clinically significantly abnormal during participation in the study will be repeated until the values return to normal or baseline or are no longer considered clinically significant by the Investigator or Medical Monitor.
 - If such values do not return to normal/baseline within a period of time judged reasonable by the Investigator, the etiology should be identified, and Alexion notified.
 - If laboratory values from non-protocol-specified laboratory assessments performed at the institution's local laboratory require a change in participant management or are considered clinically significant by the Investigator (eg, SAE or AE or dose modification), then the results must be recorded in the eCRF.

The maximum total blood volume collected from participants in the study will not exceed 500 mL in 16 weeks. The American Red Cross at the time of completion of this protocol (https://www.redcrossblood.org/faq.html) states that people can give up to 470 mL every 56 days. Therefore, the 500 mL per 16 weeks permitted in this study is approximately consistent with current clinical practice.

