For the summary statistics of all continuous variables unless otherwise specified, for absolute value, minimum and maximum will be presented to the same number of decimal places as the raw data, mean, median, Q1, Q3, and IQR will be presented to one more decimal places than the raw data, SD will be presented to two more decimal places than the raw data; for percent change, minimum and maximum will be presented to one decimal place, mean, median, Q1, Q3, and IQR will be presented to two decimal places, and SD will be presented to three decimal places. %CV and geometric %CV will be presented to one decimal place, and N and n will be presented to integer.

Percentages will be suppressed when the count is zero and will be presented to one decimal place. The denominator for all percentages will be the number of participants in the cohort for the population of interest, unless otherwise specified.

All tables, listings, and figures will be presented by cohort, unless otherwise specified.

All data listings will be sorted by cohort, participant number, and date-time if applicable.

No algorithm for imputation of missing data will be employed but will be analyzed as missing.

Study days are calculated with respect to the first dose date as below:

- If the assessment/observation date is on or after the first dose date, then Study Day = Assessment/Observation Date First Dose Date + 1;
- Otherwise, Study Day = Assessment/Observation Date First Dose Date

Study weeks are calculated with respect to the first dose for the assessment/observation occurred on or after the first dose as below, unless otherwise specified:

• Study Week = Integer part of (Assessment/Observation Date – First Dose Date)÷7+1

Baseline will be defined as the last non-missing assessment (including repeated and unscheduled assessments) before the first dose of study drug administration, unless otherwise specified.

For summary of safety assessments, if there are repeated measurements at a time point, the first non-missing assessment at that time point will be used in the summary tables.

Unscheduled results will not be included in the summary tables, except for determining Baseline, but will be presented in data listings.

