Summary statistics and change from baseline for chemistry, hematology, coagulation, and urinalysis will be presented by relative time to dose. Laboratory parameter values will be graded based on the National Cancer Institute CTCAE (v5.0, published 27 Nov 2017) grading for severity. Shift tables will be produced for chemistry, hematology, coagulation, and urinalysis. Shift from baseline grade tables will be presented by relative time to dose. Shift from baseline to post-baseline worst highest grade will be presented.

All clinical laboratory tests (including chemistry, hematology, coagulation, and urinalysis) will be presented in data listings.

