Summary statistics and change from baseline for vital signs (temperature, respiratory rate, pulse, and systolic and diastolic blood pressure) will be presented by relative time to dose.

Vital sign measurement results, including height, weight, and BMI, will be presented in a data listing.

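### SAP Section 4 takes the last reading at baseline but the first after dosing, which builds a small false cohort-level change into blood pressure and pulse

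*SAP*

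**What the plan says.** SAP Section 4 sets three general rules.

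- Baseline: "Baseline will be defined as the last non-missing assessment (including repeated and unscheduled assessments) before the first dose of study drug administration".
- Safety summaries: "if there are repeated measurements at a time point, the first non-missing assessment at that time point will be used in the summary tables".
- Unscheduled values: "Unscheduled results will not be included in the summary tables, except for determining Baseline".

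The protocol ties repeats to the result. Section 8.2.2 reads: "Out of range blood pressure or pulse measurements will be repeated at the Investigator's discretion". For laboratory tests, Section 8.2.4 says that "values considered clinically significantly abnormal during participation in the study will be repeated until the values return to normal or baseline", or until they are no longer judged clinically significant.

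The rules feed the change-from-baseline tables in SAP 9.3 ("Summary statistics and change from baseline for vital signs") and SAP 9.2 ("Summary statistics and change from baseline for chemistry, hematology, coagulation, and urinalysis will be presented by relative time to dose"). Neither section replaces the general rules. SAP 9.5 does so for ECG, where triplicates are averaged and baseline has its own definition.

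**The concern.** Suppose a participant has a high systolic reading and the repeat is normal. Before the first dose, the normal repeat becomes baseline. At a post-dose visit, the same pair of readings enters the table as the high one. Because repeats are triggered by abnormal first readings, the baseline column is filtered and the post-dose columns are not. Their difference need not average zero when the drug does nothing.

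The study is open-label with no randomization or control group, so no comparison arm carries the same artefact. Cohorts have about five participants, so one replaced reading can visibly move a cohort mean or maximum. At stake is how the vital-sign tables are read, not a test or a power calculation.

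**Working it through.** The plan has no figure to reproduce. SAP 4.1 states no hypotheses and SAP 4.2 calls the sample size empiric. The check asks what the two rules produce when there is no drug effect.

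**Inputs.** The two rules come from SAP Section 4 and the repeat trigger from Protocol 8.2.2. The documents give no SDs, no limit and no repeat frequency, so these are assumed: systolic limit L = 140 mmHg (upper side only), between-person SD 12, within-person SD w = 6 to 10, population mean μ = 125 to 135. A fraction q of readings above L is repeated once, regardless of how far above L they lie.

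**Mean shift.** Let s = √(12² + w²) and z = (L − μ)/s, with φ and Φ the standard normal density and distribution function. A first reading above L exceeds its own repeat by an expected amount which, averaged over the whole cohort, is (w²/s)·φ(z). Baseline is lowered by q times that amount and the post-dose value is not, so

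false mean change = q · (w²/s) · φ(z).

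For μ = 130, w = 8: s = √(144 + 64) = 14.42; z = 10/14.42 = 0.693; φ(z) = 0.3137; w²/s = 64/14.42 = 4.438. With q = 1 the shift is 4.438 × 0.3137 = 1.39 mmHg.

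| μ, w | z | φ(z) | w²/s | Shift, q = 1 | q = 0.5 | q = 0.25 |
|---|---|---|---|---|---|---|
| 120, 8 | 1.387 | 0.1525 | 4.438 | 0.68 | 0.34 | 0.17 |
| 125, 8 | 1.040 | 0.2323 | 4.438 | 1.03 | 0.52 | 0.26 |
| 130, 6 | 0.745 | 0.3022 | 2.683 | 0.81 | 0.41 | 0.20 |
| 130, 8 | 0.693 | 0.3137 | 4.438 | 1.39 | 0.70 | 0.35 |
| 135, 10 | 0.320 | 0.3790 | 6.402 | 2.43 | 1.21 | 0.61 |

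Simulation of these settings agreed to within about 0.02 mmHg. The four settings with μ = 125 to 135 give +0.8 to +2.4 mmHg at q = 1. At q = 0.25 to 0.5, w = 8 and μ = 120 to 130, the range is about +0.2 to +0.7 mmHg.

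**Who carries it.** In participants repeated at baseline, the second pre-dose reading and the first post-dose reading are both unselected draws around the same true mean, so their expected change is 0 (simulated −0.04 to +0.05 mmHg). In the rest, the retained baseline is truncated at 140. At q = 1 their mean change is the shift divided by Φ(z): 0.81/0.772 = 1.05 mmHg at (130, 6) and 2.43/0.626 = 3.88 mmHg at (135, 10).

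**Out-of-range rate.** Across the four settings with μ = 125 to 135 at q = 1, the simulated share above 140 is 7.7 to 23.3% at baseline and 14.9 to 37.4% after dosing, with no drug effect.

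**Dependence on distance from the limit.** For one person whose true mean lies d within-person SDs below a single limit, the shift at q = 1 is φ(d) SDs: 0.40 at d = 0, 0.24 at 1, 0.05 at 2 and 0.004 at 3. If the mean sits midway between two limits, the mean shift is 0. The out-of-range excess p − p² remains: with limits 1 SD away, p = 0.317 and the excess is 0.217; with limits 2 SD away, p = 0.046 and it is about 0.04.

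**Same rule on both sides.** First/first and last/last both returned a mean change within 0.02 mmHg of 0 and equalise the expected out-of-range rates.

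**The case against.** Much of the case on the other side stands.

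- **The size is uncertain and may be small.** Repeats are discretionary and no threshold is set. With five participants, the standard error of a mean change in this model is about 3.7 to 6.2 mmHg, larger than the shift. That makes the shift hard to see; it does not justify building it in.
- **Laboratory values.** A reader might infer that laboratory changes are biased in the same way. The documents support this only narrowly. The trigger in Protocol 8.2.4 is clinical significance, not merely being out of range. Routine panels are drawn at Screening and again on Day -1, so a Screening repeat is normally superseded. The effect needs a clinically significant Day -1 result redrawn before the Day 1 dose. Where that happens, it also reaches the shift table: "Shift from baseline to post-baseline worst highest grade will be presented".
- **Every change from baseline.** A reader might infer this too. ECG has its own averaging and baseline definition, and the first-reading rule is confined to safety assessments, so pharmacodynamic endpoints fall outside the pair.
- **Repeated participants.** A reader might also infer that people with out-of-range baseline readings show a large false rise. In the four main settings their first and second pre-dose readings differ by about 3.5 to 6.9 mmHg on average, but no planned table reports that gap, and their change from baseline averages about 0.
- **Consequence.** The primary endpoint is the incidence of TEAEs and TESAEs, which does not use these tables. Confirmed, clinically significant vital signs become adverse events under Protocol 8.2.2, and repeats appear in listings. SAP 9.3 plans no out-of-range or shift table for vital signs, so there the excess shows through means, maxima and individual changes. The artefact overstates abnormality; it does not hide it.

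None of this removes the mismatch for blood pressure and pulse, and nothing in SAP 9.3 overrides it.

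**Conclusion.** The point holds as a minor inconsistency in an analysis rule. Followed exactly, SAP Section 4 gives a false cohort-level mean shift toward the abnormal side when values lie near one limit, and a false rise in the out-of-range rate, with no control arm to reveal either. The systolic shift is +0.8 to +2.4 mmHg if every high reading is repeated (mean 125 to 135, between-person SD 12, within-person SD 6 to 10, limit 140), and about +0.2 to +0.7 mmHg at 25 to 50% repeated (mean 120 to 130, within-person SD 8). All these inputs are assumptions. The existence of the effect follows from the text; its size does not. Blood pressure and pulse are the main case. The documents do not support extending it to laboratory data in general, to ECG, to pharmacodynamics or to the primary endpoint.

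**What to change.** In SAP Section 4, apply one repeat rule to safety assessments on both sides. The simplest version defines their baseline as the first non-missing reading at the last scheduled pre-dose time point with data, which matches the existing post-dose rule. Using the last reading or the mean on both sides works equally well, but the exclusion of unscheduled results would then need adjusting wherever post-dose repeats are recorded as unscheduled. Leave the ECG rule as it is and keep all repeats in the listings.

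The cost is one sentence, with no new data or design change. A common rule brings the cohort mean change to zero under no effect. It does not stop regression to the mean in a subgroup picked for high baseline values, so such subgroups still need cautious reading. Letting worst-grade tables draw on every post-dose value is a separate question, would conflict with the exclusion of unscheduled results, and is not proposed here.

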8.2.3.1. Safety Review of 12-lead Electrocardiograms

All recorded ECGs will be reviewed by the Investigator or qualified designee. If a participant shows a clinically significant abnormal ECG, additional safety recordings may be made, and the abnormality will be followed to resolution.

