9.4.2. Safety Analyses

The primary objective of the study is to assess the safety and tolerability of ALXN1850. The endpoints to support the primary objective include incidence of TEAEs and treatment-emergent serious adverse events (TESAEs). The incidence of TEAEs and TESAEs will be summarized by System Organ Class (SOC) and Preferred Term by administration and cohort overall, by severity, and by relationship to study intervention. Adverse events will be categorized by the type of administration being received at the date of onset (ie, IV or SC). Treatment-emergent AEs and TESAEs resulting in withdrawal from the study will be listed. Participants having multiple AEs within a category (eg, overall, SOC, Preferred Term) will be counted once in that category. For severity tables, a participant's most severe event within a category will be counted. Adverse events of special interest will be analyzed similarly.

Changes from baseline in vital signs and laboratory assessments (as displayed in Table 7) will be summarized by visit for each cohort. Laboratory parameter values will be graded based on the National Cancer Institute CTCAE grading for severity (v5.0, published 27 Nov 2017). Shift tables by treatment group will be produced for these laboratory parameters. These tables will summarize the number of participants with each baseline grade relative to the normal ranges and changes to the worst highest grade assessed postdose during the study.

Electrocardiogram parameters will be measured at the specified time points, including heart rate, PR, RR, QRS, QT, and QTcF intervals. The average of the triplicate ECG readings at the time points collected will be calculated, and changes from pretreatment baseline values will be assessed.

An outlier analysis will be performed that will summarize the frequency and percentage of participants who meet any of the following outlier criteria at each visit.

- QT, QTcF interval > 450 msec
- QT, QTcF interval > 480 msec
- QT, QTcF interval > 500 msec
- QT, QTcF interval increases from baseline > 30 msec
- QT, QTcF interval increases from baseline > 60 msec

Physical examination results will be classified as Normal, Abnormal Not Clinically Significant (NCS), Abnormal Clinically Significant (CS), and Not Examined. The results will be summarized by visit for each administration.

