- Pre SC dose 3, 2 hours post SC dose 3, 6 hours post SC dose 3, 12 hours post SC dose 3, 24 hours post SC dose 3, 48 hours post SC dose 3, 1 week post SC dose 3, and 8 weeks post SC dose 3.

Summary statistics and changes from baseline of calculated average for heart rate, PR, RR, QRS, QT, and QT interval corrected for heart rate using Fridericia's formula (QTcF) will be presented by relative time to dose and by each dose.

An outlier analysis will be performed. Summary table showing the frequency and percentage of participants who meet any of the following criteria at each relative time to dose will be produced.

• QT, QTcF interval:

- \circ $\leq 450 \text{ msec}$
- \circ > 450 and \leq 480 msec
- \circ > 480 and \leq 500 msec
- \circ > 500 msec
- QT, QTcF interval increases from baseline:
 - $\circ \le 30 \text{ msec}$
 - \circ > 30 and \leq 60 msec
 - \circ > 60 msec

All ECG findings will be presented in a data listing.

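### SAP Section 4 keeps unscheduled and later repeat results out of the worst-grade laboratory shift, so that table can only match or understate the worst post-dose grade

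*SAP*

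**What the plan says.** SAP Section 4 (General Statistical Considerations) sets two rules for post-dose safety data. On unscheduled results: "Unscheduled results will not be included in the summary tables, except for determining Baseline, but will be presented in data listings". On repeats: "if there are repeated measurements at a time point, the first non-missing assessment at that time point will be used in the summary tables". Neither sentence leaves room for a different rule elsewhere in the plan. The Baseline definition in the same section does leave that room, and it treats such values the other way: "Baseline will be defined as the last non-missing assessment (including repeated and unscheduled assessments) before the first dose of study drug administration".

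SAP 9.2 plans laboratory summaries and grade shifts by time relative to dose and then, separately: "Shift from baseline to post-baseline worst highest grade will be presented". It does not say which results feed that last table. Protocol 9.4.2 describes the same table as setting baseline grade against "changes to the worst highest grade assessed postdose during the study".

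The protocol also creates extra results by design. Under 8.2.4, laboratory "values considered clinically significantly abnormal during participation in the study will be repeated" until they recover or stop being clinically significant. Under 8.2.3.1, after a clinically significant abnormal ECG, "additional safety recordings may be made". For QT and QTcF, SAP 9.5 tabulates the "frequency and percentage of participants who meet any of the following criteria at each relative time to dose", and protocol 9.4.2 asks for the same outliers by visit.

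**The concern.** A table labelled worst post-baseline grade should show the highest grade each participant reached. Under Section 4 it shows the highest grade among the scheduled first values. A result taken between visits, or a repeat that comes back worse, is left out and appears only in a listing. The possible error runs in one direction, towards a milder laboratory picture.

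The two sides of the shift are also treated differently. Before dosing, repeats and unscheduled values count and the last one is used. After dosing, unscheduled values do not count and the first of any repeats is used. An unscheduled value can set the starting grade but never the worst grade.

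At stake is whether the one laboratory table meant to capture worst toxicity delivers what the protocol describes, in a first-in-human study with about 5 participants per dose.

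**Working it through.** The plan states no figure on this point and tests no hypothesis, so there is nothing to reproduce. The check sets the rules side by side, works out their direction, and sizes one case.

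**1. Which results are eligible**

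| Result | Protocol 9.4.2 worst grade | SAP 9.2 worst grade under SAP Section 4 |
|---|---|---|
| Scheduled, first value | in | in |
| Later repeat at the same time point | in | out |
| Unscheduled post-dose value | in | out |

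**2. Direction.** Let A be all of a participant's post-dose grades and S the scheduled first values, so S is a subset of A. Then max(S) ≤ max(A). The SAP grade can equal the protocol grade or fall below it.

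**3. Hypothetical sequences, for illustration only**

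| Sequence of grades | SAP rule | All post-dose |
|---|---|---|
| Scheduled 2, repeat at the same visit 3 | 2 | 3 |
| Scheduled 0, unscheduled 3, next scheduled 0 | 0 | 3 |
| Scheduled 3, repeat 1 | 3 | 3 |

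The third row matters: a scheduled abnormal value that triggers a repeat stays in the table.

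**4. Where unscheduled results can fall.** Scheduled post-dose laboratory days (SAP 9.2; protocol Tables 1 and 2):
- First participants: Days 2, 8, 14, 16, 21, 23, 28, 30, 36, 65 (10 days). Gaps are 2 to 6 days up to Day 36, then 65 − 36 = 29 days.
- Subsequent participants: Days 2, 7, 9, 14, 16, 21, 23, 29, 57 (9 days). Gaps are 2 to 6 days up to Day 29, then 57 − 29 = 28 days.

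No routine safety laboratory visit follows end of treatment. Routine results in the remaining 85 − 65 = 20 days (first) or 78 − 57 = 21 days (subsequent) before end of study would therefore be unscheduled too.

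**5. Weight of one participant.** SAP Section 4 takes percentages over the participants in the cohort for the population of interest, here the Safety Set. With the planned number of about 5 per cohort, 1/5 = 20.0 percentage points. Over about 15 in total, 1/15 = 6.7 points.

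**The case against.** The strongest reply has five parts.

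- **The specific section may govern.** The word worst in SAP 9.2 could be read as implying all data. That may be the intent, but the SAP does not say so, and a programmer following Section 4 would exclude the values. The ambiguity alone justifies a clarification.
- **Most excluded follow-up shows recovery.** A reader might infer that the tables drop the very results taken because something looked abnormal. The documents do not support that. The scheduled value that prompted the repeat is kept, and repeats continue until the abnormality settles. Event-triggered hypersensitivity laboratory tests have their own summary time points in SAP 9.8. What is lost is narrower: a worse follow-up value, or an abnormality first seen off schedule.
- **The adverse event route.** A reader might also infer that the primary safety result is biased. The primary endpoint is the incidence of TEAEs and TESAEs. Clinically relevant laboratory changes go into the AE record (protocol 8.2.4 and 10.3.1), and AE tables use the most severe event within each administration type (SAP 9.1). This stands, and the primary tables are not directly affected. It does not replace the shift table, because entry as an AE depends on the investigator's judgement of clinical significance and the laboratory grade does not.
- **Everything is listed.** True, and workable with about 15 participants. A listing still does not correct a table whose title promises more than its content.
- **QT and QTcF.** The by-time-point layout follows the protocol's by-visit request, so the SAP does not depart from it. Extra safety ECGs need not be triplicate, while SAP 9.5 summarises triplicate averages. Adding every recording would mix single readings with averages. This part stands: a row for any post-baseline time is an improvement to consider, not the correction of an error.

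**Conclusion.** The point holds for the laboratory worst-grade shift. SAP Section 4, applied as written, makes that table narrower than protocol 9.4.2 describes, and the only possible effect on the worst grade is to match or understate it. Each affected participant moves a cohort percentage by 20 points with 5 in the Safety Set, or the overall percentage by 6.7 points with 15.

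A figure of 33 points (1/3) is tempting but not supported. Three is the minimum number of completers per cohort, whereas the Safety Set counts everyone who receives any study drug, planned at about 5.

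The conclusion rests on three assumptions. Section 4 is applied literally. The end-of-treatment laboratory visit counts as scheduled and so enters the worst grade, although the list of summary time points in SAP 9.2 stops at 1 week after the third SC dose. Some participant has a worse repeat or an off-schedule abnormality; nothing in the documents indicates how often that would occur, and if it never does, the table is unaffected.

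This should be fixed because it is cheap and brings the SAP into line with the protocol. It does not put the primary analysis in doubt.

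**What to change.** Amend SAP Section 4, and repeat the rule in SAP 9.2, along these lines:

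> Summaries by time point use scheduled results only, taking the first non-missing value where a measurement is repeated. The shift from baseline to worst post-baseline CTCAE grade uses all post-dose results, including repeat and unscheduled results and the end-of-treatment visit.

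By-time-point statistics stay as planned. The change uses data already collected and listed, and costs a sentence or two and minor programming.

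Optionally, add an any-post-baseline row to the QT/QTcF outlier table in SAP 9.5. The present layout does not show how many participants ever cross a threshold. Its list of summary times also goes from 1 week to 8 weeks after the third SC dose, leaving no row for the scheduled end-of-treatment ECG. Build the row from triplicate averages, scheduled and unscheduled, and list single unscheduled recordings separately so that they are not mixed with averages. The cost is one row, the rule for single recordings, and some extra programming.
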